2.2.3 Exploratory Endpoints

first CV event

occurrence of the composite MACE endpoint in the subgroup of patients that survived the

Time from first adjudicated non-fatal MACE to a second confirmed (adjudicated)

Page 13 of 51

3 Trial design

The following section details the original trial design. However, the trial was terminated due to feasibility problems, with only 545 patients randomized and 14 of those with positively adjudicated events. Hence, many of these sections no longer apply.

3.1 General Design Considerations

This is a multi-center, randomized, assessor-blind, controlled trial to compare MACEs in patients with prostate cancer and concurrent CVD receiving either monthly treatment with degarelix or leuprolide 3-month depot for 1 year. Patients will be screened within 8 to 21 days prior to randomization for compliance with the inclusion and exclusion criteria. A trial design diagram is provided in Figure 1.

[figure not shown]

Figure 1 Trial Design Diagram

Patients will be randomized to one of the two treatments in a 1:1 ratio stratified by age group (<75 and ≥75 years of age) and region (North America, other). After randomization, the management of prostate cancer is intended to reflect standard-of-care. Monitoring for possible MACEs will occur throughout the trial applying a specific Clinical Events Classification (CEC) process ensuring blinding of the event assessors.

3.2 Determination of Sample Size

The primary objective is to assess the effect of degarelix on the risk of MACEs (a composite of death due to any cause, non-fatal myocardial infarction or non-fatal stroke) occurring during a 1-year period as compared to treatment with leuprolide in patients with prostate cancer and concomitant CVD.

The observed one-year event rates for primary MACE endpoint are 5.3% and 12.1% for degarelix and LHRH agonist, respectively, in the global patient population with prior CVD were derived from a post-hoc analysis of degarelix safety data. This would correspond to an unadjusted treatment-

Date: 24 Feb 2021 E-Statistical Analysis Plan-19595; Ver.7.0 Supersedes: 6.0 Page 14 of 51

related hazard ratio of 0.42. (In comparison, the adjusted hazard ratio is 0.39 (95% confidence interval [CI] = [0.21; 0.71]).) Furthermore, based upon the re-assessment of the potential CV events captured in the degarelix safety data by an independent cardiologist, the one-year event probability for CV event or death due to any cause are 4.8% and 9.3% for degarelix and leuprolide respectively. This corresponds to an unadjusted hazard ratio of 0.50 (in comparison, the adjusted hazard ratio is 0.48 (95% confidence interval is [0.23,0.87]). Accounting for the uncertainty in the post-hoc analysis of the global pooled data and the re-assessment of the potential CV events by a single independent cardiologist, the one-year event rates for sample size calculations are set to 5.1% and 10.2% for degarelix and leuprolide, respectively. This corresponds to a hypothesized hazard ratio of 0.49.

3.2.1 Fixed Trial Design

Given the alternative hypothesis, a power of 80% and a signficiance level of 5%, the expected number of events required at the final analysis is 61. The sample size required for achieving this number of events assumes that all patients are followed-up for primary outcome (MACEs) for 12 months (28 days each) after start of treatment and an annual drop-out rate of 5%. Assuming these characteristics a total sample size of 811 patients is required.

3.2.2 Adjustments for Futility Analyses

One interim analysis is planned after 50% of the confirmed, adjudicated MACE endpoints have been collected. One of the objectives of the interim analysis is to test whether there is any reason to stop early for futility. The futility bound expressed in terms of the hazard ratio is 0.78. That is, if the observed hazard ratio is >0.78 the Data and Safety Monitoring Board (DSMB) may suggest to stop the trial due to futility. The futility bounds are non-binding. Due to the possibility to stop early for futility the power is deflated (risk of stopping a successful trial is inflated), and to reinstall the power at 80% the number of required events is inflated to 66 and the total number of patients to 876.

The trial will not be stopped early due to an overwhelming treatment benefit, but in order to implement the trial design, an alpha-spending function will be used with nearly zero spending of alpha at the interim analysis, $\alpha < 0.0001$ (e.g. trial will not be stopped early for efficacy).

3.2.3 Adjustments for Sample Size Re-Estimation

The conditional power for different sample size increases will be evaluated at the interims using SAS. In case of a sample size increase, the final test statistic is adjusted by using the normal inverse method in order to protect the two-sided Type I error rate at 5%.

The sample size calculations are performed with ADDPLAN™ 6, licensed by ADDPLAN, Inc., an Aptiv Solutions company and presented in Table 1.

Page 15 of 51

Table 1 Sample Size Calculations (Number of Events Rounded Upwards)

Information Rate	Stop for futili	ty/No eviden	ce reject H ₀	Successful trial (Reject H ₀₎	g gnant	Power	Events
	Test Statistic	Hazard Ratio	Conditional Power	Test Statistic	α spent		
50%	≤ 0.7	≥0.78	≤8.5%	-	< 0.0001	-	33
100%	≤1.96	≥0.61	-	≥ 1.96	0.025	80%	66

- Assuming constant hazards, $\lambda_{degarelix} = 0.0523/year$ $\lambda_{leuprolide} = 0.1076/year$
- 5% drop out rate in each arm
- 1:1 randomization ratio

When d, the number of events, has been observed, the approximate relationship between the standardized test statistic, Z, and the hazard ratio (HR) as given in (Jennison and Turnbull, 2000) is,

$$Z \approx log(HR^{-1})\sqrt{d/4}$$

For reasons of interpretation, both Z and the hazard ratio are reported in design tables.

Date: 24 Feb 2021 E-Statistical Analysis Plan-19595; Ver.7.0 Supersedes: 6.0 Page 16 of 51

4 Patient Disposition

All patients screened and randomized will be accounted for. All post-randomization discontinuations will be summarized by time of, and reason for, discontinuation. The number of patients screened and not randomized will be presented with the reason(s) for screen failure.

Special attention should be paid to those patients who discontinue treatment with investigational medicinal product (IMP) and start an alternative treatment during the trial, including the dates corresponding to going off the randomized drug, i.e. the date of the last injection and the start of a new treatment, i.e. the date the new treatment was initiated.

In addition, the breakdown of the overall disposition of patients by age group (<75 years of age, ≥75 years of age) and region following the design (stratification) of the trial will be provided. Also, the number of patients screened and randomized, overall and by age group (<75 years of age, ≥75 years of age) and region will be provided.

1- Kaplan–Meier (1-KM) plots of the time to early discontinuation, as well as the time to treatment discontinuation or initiation of prohibited therapies related to hormonal therapy, will be displayed per treatment arm. In addition, time to early discontinuation by reason for discontinuation and treatment arm will be presented by cumulative incidence function curves. Differences in discontinuation rates and treatment discontinuation or initiation of prohibited therapies related to hormonal therapy rates between treatment groups will be tested using the Log Rank test (α =0.05, two-sided).

Date: 24 Feb 2021 E-Statistical Analysis Plan-19595; Ver.7.0 Supersedes: 6.0

Page 17 of 51

5 Protocol Deviations

As no PP analyses are planned, there will be no classification of 'minor'/'major' events, reflecting potential impact on efficacy endpoints due to protocol violations.

In order to reflect general (i.e. not specifically related to impact on efficacy) protocol adherence important deviations will be summarized by treatment group and category, and listed by subject for the Full Analysis Set.

Page 18 of 51

6 Analysis Sets

6.1 Intention-To-Treat Analysis Set

The Intention-to-Treat (ITT) analysis set consists of all randomized patients, and will be analysed based on the planned (randomized) treatment.

6.2 Full Analysis Set

The Full Analysis Set (FAS) consists of all randomized and treated patients (who received at least one dose of IMP), and will be analysed based on the planned (randomized) treatment.

6.3 Safety Analysis Set

The Safety analysis set consists of all treated patients (who received at least one dose of IMP), and will be analysed based on the actual treatment received.

Page 19 of 51

7 Trial Population

All tables will be presented for the FAS.

7.1 Demographics and Other Baseline Characteristics

Categorical data will be summarized using numbers and percentages. The percentages are based on the total number of patients with a corresponding assessment. Continuous data will be presented, for example, using the number of patients (N), mean and standard deviation, median, minimum and maximum. All baseline characteristics will be listed.

7.1.1 Demographics

7.1.2 Vital Signs at Baseline

7.1.3 History and Stage of Prostate Cancer

A summary table of history and stage of PCA will be presented, containing the following information:

- Gleason score (as defined below)
- Stage of prostate cancer (TNM classifications, as defined below)
- ECOG performance score

The following pathological stages will be recorded and summarized by treatment group, age (<75 years and ≥ 75 years) and region:

The Gleason score is calculated as the sum of the Gleason grade of the primary and secondary patterns. The following categories will be presented:

- 2-4
- 5-6
- 7-10

The stage of prostate cancer, based on the TNM classification, includes the following categories:

• Localised: T½ & (NX or N0) & M0,

• Locally Advanced: [T³/₄ & (NX or N0) & M0], or [N1 & M0],

• Metastatic: M1

•	Not classifiable:	Results from T, N, and M categories that could not be resolved to Localised, Locally Advanced, or Metastatic
1.5		cy / Pharmacodynamic Parameters at Baseline
seli	ne variables will be s	ummarized by treatment, age (<75 years and ≥75 years) and region.

Date: 24 Feb 2021 E-Statistical Analysis Plan-19595; Ver.7.0 Supersedes: 6.0

Page 21 of 51

7.4 Physical Examination

Patients with abnormalities at any screening, baseline, or post-baseline visit will be listed with all physical examination evaluations.

Page 22 of 51

8 Exposure and Treatment Compliance

All tables will be presented for the FAS.

8.1 Extent of Exposure

The cumulated dose administered to each patient will be determined and summarized descriptively. For patients discontinuing the trial early, are lost to follow-up or initiate treatment with an ADT other than Degarelix or Leuprolide, their cumulated dose will be calculated up until the time of early discontinuation/lost to follow-up/treatment iniation.

8.2 Treatment Compliance

Treatment compliance will be presented from data listings. Patients not receiving the scheduled dose will be listed by center, sorted by treatment group and patient number.

Page 23 of 51

9 Efficacy

The following sections detail the planned analyses in the protocol. Any changes to the planned analysis in the protocol are described in Section 12.

[figure not shown]
9.1 General Considerations

The analysis of efficacy will be performed for the FAS (unless otherwise specified). For the purpose of this CV outcome study, patients prematurely discontinuing from treatment will be followed-up for the occurrence of MACE events based on monthly telephone interviews. Unless otherwise stated, time to event endpoints will be censored at the time of treatment discontinuation, initiation of prohibited therapies related to hormonal therapy, lost to follow-up/withdrawal from the study or day 336, whichever occurs first. Initiation of prohibited therapy related to hormonal therapy includes the following:

- Surgical castration or other hormonal manipulation in addition to the IMPs
- Anti-androgens for combined androgen blockade (anti-androgen use for initial flare protection is allowed for a maximum period of up to 28 days after randomization)
- Estrogens
- Megestrol acetate
- Ketoconazole
- Abiraterone
- Enzalutamide
- Any additional hormonal therapy initiated as a combination therapy with the IMP

The associated ATC and MedDRA codes for the above prohibited therapies are provided in Table 11 and Table 12. Hypothesis tests will be two-sided at a significance level of 5% and missing data will not be imputed. 95% confidence limits and the associated p-values will be presented for estimates of the treatment effect comparing degarelix to leuprolide for all regression analyses.

For the purposes of	this trial,		
_			
			•

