## 6.6 End-of-Trial Visit / Visit 14 (Month 12)

Patients should be called in for an end-of-trial visit after 336 days of participation in the trial.

The following must take place at the End-of-Trial visit:

- IPSS
- PRO (DASI, CAQ and EQ-5D-5L)
- Health economics (CV-related hospitalization events, CABG/PCI procedures and ER visit events)
- 12-lead ECG
- Vital signs (pulse and blood pressure)
- Blood collection for central laboratory analysis of:
  - Testosterone (*Note: Not in patients who have discontinued treatment with IMP and have performed an end-of-treatment visit.*)
  - PSA (*Note: Not in patients who have discontinued treatment with IMP and have performed an end-of-treatment visit.*)
  - Clinical chemistry and hematology parameters
  - Glycemic and metabolic parameters (*Note: The blood samples must be taken while the patient is in fasting state, i.e. minimum of 8 hours without caloric intake.*)

- Urinalysis (dipstick)
- Body weight, waist and hip circumference

- Physical examination
- Radiographic imaging (bone scan). (Imaging can be performed up to 7 days before the End-of-Trial visit.)
- Drug accountability
- Recording of any change in use of concomitant medication
- Recording of adverse events, including CV-related signs
- Completion of End-of-Trial form

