## ***Radiographic Imaging***

A bone scan follow-up will be performed in all patients at the End-of-Trial visit (or End-of-Treatment visit) as part of the PFS endpoint. The bone scan can be performed up to 7 days before the actual visit.

In addition, radiographic imaging (e.g. bone scan, MRI or CT performed as per standard clinical practice at the discretion of the Investigator) may be conducted in order to confirm suspected metastases as part of the PFS endpoint during the trial.

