## **9.6 Endpoint Assessments**

### **9.6.1 General Considerations**

The analysis of efficacy will be performed for the FAS. Unless otherwise specified, time to event endpoints will be censored at the time of treatment discontinuation, initiation of prohibited therapies related to hormonal therapy, lost to follow-up/withdrawal from the trial or Day 336, whichever occurs first. In addition, all hypothesis tests will be two-sided at a significance level of 5% and missing data will not be imputed. 95% confidence limits and the associated p-values will be presented for estimates of the treatment effect comparing degarelix to leuprolide for all regression analyses. P-values will be presented for all non-parametric tests, such as the log-rank test.

All regression models analyzing the time to MACE or the time to components of the MACE composite endpoint will be adjusted for the following CV risk factors measured at baseline: waist circumference, body mass index (BMI), [REDACTED] blood pressure, diabetes status, cholesterol and triglyceride levels. All semi-parametric and non-parametric models will be stratified by baseline age group and region.

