9.3.6 Time from Randomization to Failure in Progression-Free Survival

Progression-free survival (PFS) is a composite endpoint consisting of the following conditions:

- Death
- Radiographic disease progression defined as one or more new metastatic skeletal lesions observed on bone scan; one or more new metastatic extra-skeletal lesions at least 1.5 cm in greatest dimension visible on computed tomography or magnetic resonance imaging scan as confirmed by the Investigator.
- Introduction of additional therapy related to prostate cancer treatment including radiation, anti-androgens and second-line treatment. (ATC and MedDRA codes for disease progression are included in Appendix 3)
- PSA failure defined as the time from randomization to the second occasion (must be at least two weeks apart from the first and correspond to consecutive measurements) in which the PSA value fulfills the following criteria:
 - I. An absolute increase of ≥ 5 ng/ml above nadir and
 - II. An increase of > 50 % of nadir

Time to PFS failure is therefore defined as the time, measured in days, from randomization to the first occurrence of one of the above composite endpoint criteria. Patients discontinuing from treatment/withdrawn from the study will be censored at the time of discontinuation/withdrawal. Time to PFS failure will be analyzed using the Kaplan-Meier estimator of the survival function, the Cox regression model for the hazard rate and the log-rank test of the null hypothesis of equal hazard functions, stratified by age group and region. The p-value of the two-sided stratified log-rank test with significance level of 5% will be presented along with plots of the estimated survival functions for the two treatment groups, stratified by age group and region. The estimated hazard ratio and the associated 95% confidence interval and p-value comparing the treatment with Degarelix to Leuprolide will also be presented.

TLF Table: Secondary Endpoint: Time to PFS Failure - FAS

TLF Figure: Survivor Function for Time to PFS Failure - FAS

Page 30 of 51

9.3.7 Testosterone levels at day 28, 168 and 336 in patients treated with degarelix and leuprolide

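### By default PFS is censored at Day 336, yet the Visit 14 bone scan and confirming PSA may validly fall as late as Day 343 and would then not count

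*SAP*

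**What the plan says.** **Cut-off.** SAP 9.1 sets the default: "Unless otherwise stated, time to event endpoints will be censored at the time of treatment discontinuation", start of prohibited hormonal therapy, "lost to follow-up/withdrawal from the study or day 336, whichever occurs first". Protocol 9.6.1 has the same rule, ending "lost to follow-up/withdrawal from the trial or Day 336, whichever occurs first".

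**PFS rule.** SAP 9.3.6 adds one censoring sentence: "Patients discontinuing from treatment/withdrawn from the study will be censored at the time of discontinuation/withdrawal". It does not mention Day 336. Protocol 9.6.3.7 gives no PFS-specific censoring rule. SAP 9.3.6 dates PSA progression at confirmation: "PSA failure defined as the time from randomization to the second occasion".

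**Assessments.** Under Radiographic Imaging the protocol says: "A bone scan follow-up will be performed in all patients at the End-of-Trial visit (or End-of-Treatment visit) as part of the PFS endpoint". It adds: "The bone scan can be performed up to 7 days before the actual visit". PSA is drawn every three months, at Visits 5, 8, 11 and 14 (nominal Days 84, 168, 252 and 336). Protocol Table 1 gives Visit 14 as Day 336 with a window of 7 days either side, counted from Visit 2, when randomization takes place (Protocol 4.2.2). Protocol 6.6 adds: "Patients should be called in for an end-of-trial visit after 336 days of participation in the trial".

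**The concern.** A fixed cut-off at Day 336 suits MACE, because a heart attack, stroke or death is dated when it happens. Radiographic and PSA progression are known only on the day someone looks. For a patient who stays on treatment, the scheduled looks that matter most come at the very end: the single follow-up bone scan and the last PSA. If the clock stops at Day 336 while the visit may run to Day 343, two men with the same new bone lesion can be scored differently because of their appointment dates.

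The plan would then collect assessments for the PFS endpoint at a protocol-compliant visit and discard some of them. A stated objective is to evaluate PFS failure rates in each group, and those rates would be too low. Events also matter more now that SAP section 3 reports 545 patients randomized, against the 876 in the sample size calculation.

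**Working it through.** **Step 1. The plan's own figure.** Protocol, Duration of Treatment: 12 treatment months of 28 days, 12 × 28 = 336 days. This reproduces. The documents state no event count, power or visit-date distribution for PFS.

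**Step 2. Visit 14 days after the cut-off.**
- Window: 336 − 7 = 329 to 336 + 7 = 343, which is 343 − 329 + 1 = 15 permitted days.
- Days after the cut-off: 337 to 343, which is 7 days.
- Share of permitted days: 7/15 = 46.7%.

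**Step 3. PSA.** The confirming value must be consecutive and at least two weeks after the first. A rise first seen at Visit 11 (Day 252) is therefore confirmed on schedule only at Visit 14. Example: Visit 14 on Day 339 is 339 − 252 = 87 days later, so the PSA criterion is met, but 339 > 336 and the patient is censored at Day 336. PSA has no allowance for an earlier draw. If visits are spread evenly over the 15 days (an assumption), 7/15 = 46.7% of Visit 14 PSAs are late.

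**Step 4. Bone scan.** The documents do not say which date defines radiographic progression; I assume the scan date. Let *v* be the visit day minus 336 (−7 to +7) and *l* the lead of the scan before the visit (0 to 7 days). The scan is late when *v* − *l* > 0. For each *v* from 1 to 7 exactly *v* of the 8 lead values meet this, so the number of late pairs is 1 + 2 + … + 7 = 28 out of 15 × 8 = 120.

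| Visit 14 assessment, visits even over Days 329–343 | Late share |
|---|---|
| PSA | 7/15 = 46.7% |
| Scan on the visit day (*l* = 0) | 7/15 = 46.7% |
| Scan lead even over 0–7 days | 28/120 = 23.3% |
| Scan always 7 days before (*l* = 7) | 0/15 = 0% |

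**Step 5. What the shares measure.** They are shares of Visit 14 assessments dated after Day 336. A PFS event is lost only if the patient had no earlier PFS event, the finding was first established at Visit 14, and the assessment was late. For PSA, the first qualifying rise must also have been at Visit 11.

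**The case against.** The strongest reply is that SAP 9.3.6 has its own censoring sentence, so it replaces the default in 9.1 and Visit 14 findings inside the window count. Two things support this. The sentence would be redundant if the default were in force. The default also fits PFS badly: it censors at the start of drugs such as bicalutamide, abiraterone and enzalutamide (SAP Table 11), which are also listed as additional therapy or anti-androgens counting as PFS failure (SAP Tables 6 and 7). That reading is possible, but the text does not say it. Where the SAP departs from the default elsewhere, in 9.2.2.4, it says so expressly and still keeps Day 336. In the protocol there is no competing PFS sentence at all. What stands is that two programmers could build different PFS datasets, which is itself a reason to write the rule down.

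Day 336 is also used as a visit label, for example for testosterone. As a limit on days since randomization, however, it has no window.

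Other replies reduce the size. Scans may precede the visit by up to 7 days, so even a Day 343 visit can have a Day 336 scan. Unscheduled imaging for suspected metastases is allowed, and unscheduled visits may include laboratory samples. Early discontinuers have an End-of-Treatment scan, though the plan censors them at discontinuation. All of this stands.

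A reader might infer more from two places:
- **The call-in wording in Protocol 6.6.** If visits fell only on Days 336 to 343, 7/8 = 87.5% of PSAs would be late. That sets aside the first half of the Table 1 window. The similar instruction in Protocol 4.4 concerns patients who stopped treatment early. They are already censored, and those who had an end-of-treatment visit have no PSA drawn at Visit 14.
- **The open-label design.** One might infer that appointment dates, and so PFS, differ by arm. The documents do not support this: both arms have the same monthly visits and the same Visit 14 window, and neither receives study drug at Visit 14.

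**Conclusion.** The point holds on the literal text. The Day 336 limit reaches PFS by default, SAP 9.3.6 does not lift it, and 7 of the 15 permitted Visit 14 days lie beyond it. The percentages in the table rest on evenly spread visits and on radiographic progression being dated at the scan, neither of which the documents give. They should not be read as the proportion of PFS events lost, which cannot be calculated from the documents.

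The consequence is lost events, lower precision and an understated PFS failure rate. PFS is a non-key secondary endpoint outside the testing hierarchy, and no sample size rests on it. The primary MACE analysis is not touched, and there is no evidence that either arm is favoured.

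**What to change.** In SAP 9.3.6, state that the Day 336 cut-off in 9.1 does not apply to PFS and that the PFS cut-off is Day 343, the end of the Visit 14 window. A bone scan or PSA done as part of Visit 14 within its window then counts, dated at the scan or at the confirming PSA. Keep Day 336 for MACE and the other endpoints dated when the event occurs.

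The cost is a sentence or two in the SAP and a small programming change. No new data are needed and no other endpoint changes. An end-of-trial PFS estimate should then be read at Day 343. The number at risk should be shown over Days 329 to 343, since it will fall quickly if completers are censored at their own Visit 14.
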